**Part 1 and Part 2**

**Blood:** The participants in the trial will have:

**Part 1:** A maximum of 12.5ml of blood collected at baseline and 2 weeks post-injection will be sent to the NDORMS laboratories in Oxford.

**Part 2:** A maximum of 12.5ml of blood collected at baseline, 3 months, and 12 months post first injection, will be sent to the NDORMS laboratories, in Oxford.

The transportation procedure is described in the Sample Handling Manual. On arrival the serum will be stored at -80 degrees Celsius. Serum concentration of adalimumab and antibodies to adalimumab will be measured using a commercial ELISA kit.

Participants will have provided informed consent approving collection, long-term storage, and future use of tissue and blood. As new mechanisms of action, safety and efficacy may evolve during or following the trial, which are unknown at present, biospecimens will be stored for a maximum of 15 years from the end of trial, after which time they will be destroyed. All samples will be identified by a trial identification number and stored securely.

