## 4. STATISTICAL PRINCIPLES

### 4.1 Statistical Significance and Multiple Testing

There is no multiple testing as only a single primary objective is considered. Therefore, significance levels used will be 5%, and 95% confidence intervals will be reported. Secondary outcomes will also be analysed using a significance level of 5% and 95% confidence intervals as these are considered supportive of the primary conclusion only. Other outcomes will be considered exploratory and hypothesis generating only.

No interim analysis of primary and secondary endpoints are planned but, if requested by the DSMC, a 0.1% significance ( $\alpha=0.001$ ) will be used.

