## 6.2 Analysis methods: Primary outcome

The primary outcome analysis will be performed on the ITT population, comparing intervention (adalimumab) against placebo (saline, 0.9% NaCl) for all randomised participants with available nodule hardness data.

The adjusted difference in the mean change of nodule hardness between the two groups will be reported with 95% confidence intervals. The primary time point is 12 months. The primary analysis will be the comparison of change in nodule hardness between the adalimumab and saline groups using Analysis of Covariance (ANCOVA) adjusting for baseline nodule hardness, if it is normally distributed. If the data are not normally distributed, the data will be log-transformed in order to gain normality and geometric means with 95% confidence intervals reported. If data are not normally distributed after log-transformation, the non-parametric Mann-Whitney test will be used with no adjustment for baseline, and the median change with 95% confidence intervals will be reported.

As a supporting analysis, ANCOVA adjusting for baseline nodule hardness as well as the stratification factors comprising centre (Oxford, Edinburgh or Groningen) and age (as a continuous variable) will be conducted.

As a further supporting analysis, in order to analyse change in nodule hardness over the full time period, linear mixed effects regression will be used to compare nodule hardness between interventions utilising all available time-points up to 18 months and adjusting for stratification factors. Multilevel models permit all available data to be included in the analysis, thus eliminating complete case bias.

**Appendix 5: Outcome measure summaries, Table 8:** Mean (with SD) nodule hardness recorded at each study time-point.

**Appendix 5: Outcome measure summaries, Table 9:** Mean (with SD) nodule hardness at 12 months by number of injections received.

**Appendix 5: Outcome measures analysis, Table 17:** Nodule hardness ANCOVA and linear mixed-effects regression results for all follow-up time-points.

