### 6.4 Analysis methods: Tertiary and exploratory outcomes

For the analysis of circulating levels of adalimumab and antibodies to adalimumab in the blood (tertiary objective), we will report circulating levels of adalimumab by treatment arm. The mean difference between levels recorded at baseline, 3-months and 12-months in those who received at least one adalimumab injection will be explored.

Repurposing anti-TNF for treating Dupuytren's disease (funded by Health Innovation Challenge Fund, Wellcome Trust)

EudraCT Number: 2015-001780-40 and OCTRU Reference Number CTU0028

For the analysis of changes in other molecular markers and biomarkers in the blood (exploratory objective), the mean difference between levels recorded in the two treatment groups at baseline, 3-months and 12-months will be reported.

If the data are normally distributed a t-test to assess for significant differences between levels at 3-months and 12-months will be applied. If the data are not normally distributed, the data will be log-transformed in order to gain normality and geometric means with 95% confidence intervals will be reported. If data is not normally distributed after log-transformation, the non-parametric Mann-Whitney test will be used with no adjustment for baseline, and the median change with 95% confidence intervals will be reported. Where significant differences are identified, correlations between the tertiary and exploratory outcomes and the primary outcome will be carried out. Further explorations of tertiary outcomes may include: (1) additional adjustments to the primary outcome model by including circulating levels as continuous covariates, and (2) further regression modelling to directly explore associations between grouped levels – using ordered categorisation – and the primary outcome.

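### SAP 6.4 allows post-randomisation adalimumab level to enter the two-arm primary model and pooled exposure analyses; the resulting arm coefficient is not the randomised effect, so these explorations should be confined to the adalimumab arm

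*SAP*

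**What the plan says.** SAP 6.4 covers circulating adalimumab and antibodies to it (tertiary) and other markers (exploratory). After the descriptive comparisons it has three provisions that link levels to nodule hardness:

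- Correlations: "Where significant differences are identified, correlations between the tertiary and exploratory outcomes and the primary outcome will be carried out".
- Option (1), worded as a possibility: "additional adjustments to the primary outcome model by including circulating levels as continuous covariates".
- Option (2): "further regression modelling to directly explore associations between grouped levels" and the primary outcome, with the levels put into ordered categories.

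For none of these does the section say which sampling time supplies the level, whether saline participants are included, or how an arm coefficient would be read. For option (2) and the correlations it does not say whether arm is in the analysis. One population limit does appear, "in those who received at least one adalimumab injection will be explored", but it belongs to the comparison of levels between visits, not to the three provisions above.

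The model that option (1) would extend is defined in SAP 6.2. It compares the two arms in all randomised participants with hardness data, "using Analysis of Covariance (ANCOVA) adjusting for baseline nodule hardness, if it is normally distributed". Circulating level is not in it. SAP 4.1 says of outcomes other than the primary and secondary ones: "Other outcomes will be considered exploratory and hypothesis generating only".

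Under protocol 8.7, Part 2 research blood is "collected at baseline, 3 months, and 12 months post first injection". Injections are planned at baseline, 3, 6 and 9 months (SAP 3.1), so each post-baseline sample falls about three months after the previous planned injection.

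**The concern.** The comparator is saline, so a saline participant's drug level should be zero or undetectable, and a positive level can arise only through active injections. The level is thus a consequence of allocation. Once it is in the model, the arm coefficient answers a different question from the one randomisation settles: it compares an adalimumab participant with zero level against a saline participant.

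Grouped-level regressions and correlations have a different weakness. If they pool both arms without an arm term, every saline participant sits at the bottom of the level scale. Any treatment effect, by whatever route, then appears as an association with level.

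What is at stake is interpretation. A published level-adjusted version of the primary model could show an arm effect near zero, or a much less precise or biased one, and SAP 6.4 has no sentence telling the reader not to take it as a treatment effect.

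**Working it through.** **The plan's own figure.** SAP 3.3 uses a standardised effect of 0.62, two-sided 5% and 90% power: n per arm = 2(1.960 + 1.282)²/0.62² = 54.7, so 55. Allowing for 20% loss, 55/0.8 = 68.75, so 69 per arm and 138 in total, as stated. I use 55 evaluable per arm, effect -5 (negative means softer on adalimumab) and SD 8. The arm-only standard error is 8√(2/55) = 1.53.

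**Inputs the documents do not give.** The level distribution is an assumption: zero on saline; in the adalimumab arm 100%, 50% or 20% of participants measurable, with lognormal levels (mean 1, CV 0.3 to 1.0) among them. Each setting was simulated 1,500 times.

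**Arm coefficient after adjustment.** With all saline levels at zero, the saline arm carries no information on the level slope s. The adjusted arm coefficient is D - s × (mean level on adalimumab), where D is the plain difference between arms.

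- *Whole effect through the level.* With all measurable (mean level 1), s = -5, so -5 - (-5)(1) = 0. Simulated: between -0.05 and 0.10 in all nine settings, with rejection in 5 to 7% of trials.
- *Unmeasured factor affecting both level and hardness* (assumed correlation 0.5 with log level, 4-point SD on hardness, level itself inert). All measurable, CV 0.3: s = 6.69, so -5.02 - 6.69 = -11.71. At CV 0.5 and 1.0 the coefficient is -8.86 and -6.88. With 50% measurable it is -5.42 to -5.72; with 20%, -5.08 to -5.20.
- *Level irrelevant, no common cause.* The coefficient stays near -5 but loses precision. With all measurable, r² between arm and level is 1/(1 + 2CV²), so the variance inflation factor is 1 + 1/(2CV²): 6.6, 3.0 and 1.5 at CV 0.3, 0.5 and 1.0. Multiplying 1.53 by the square roots gives 3.9, 2.6 and 1.9, close to the simulated values below.

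The table is for a level with no true effect and no common cause. The last two columns give the share of trials in which that level reaches p<0.05.

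| Measurable on adalimumab | CV | Arm-level r | SE of adjusted arm coefficient | Power for arm (arm-only about 0.90) | Level, arm in model | Level, pooled, no arm term |
|---|---|---|---|---|---|---|
| 100% | 0.3 | 0.92 | 4.00 | 0.24 | 5% | 84% |
| 100% | 0.5 | 0.82 | 2.71 | 0.46 | 6% | 77% |
| 100% | 1.0 | 0.61 | 1.95 | 0.72 | 5% | 50% |
| 50% | 0.3 | 0.55 | 1.83 | 0.78 | 5% | 40% |
| 50% | 0.5 | 0.50 | 1.77 | 0.79 | 5% | 36% |
| 50% | 1.0 | 0.40 | 1.67 | 0.85 | 5% | 24% |
| 20% | 0.3 | 0.32 | 1.61 | 0.88 | 6% | 16% |
| 20% | 0.5 | 0.30 | 1.60 | 0.88 | 5% | 15% |
| 20% | 1.0 | 0.26 | 1.58 | 0.89 | 5% | 11% |

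With 20% measurable the standard error rises by about 4 to 6% (1.58/1.52 = 1.04; the largest variance inflation factor, 1.12, has square root 1.06).

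**Within-arm check.** The level slope estimated in the adalimumab arm alone equalled the level coefficient in the arm-plus-level model in every setting. These models had no baseline covariate. With pooled baseline adjustment the saline arm would still add essentially nothing to the slope.

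**Why a common cause is plausible here.** Protocol section 6, Part 2, lets the clinician omit an injection when the nodule has become too small to inject accurately. Response may therefore influence later drug level. I have not quantified this.

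**The case against.** The strongest reply is that these analyses are optional and tertiary. SAP 4.1 places them in the hypothesis-generating tier, and neither the primary model nor its supporting and sensitivity analyses use the level. The primary estimate, type I error and sample size are untouched, and nothing in the SAP presents a level-adjusted arm coefficient as a treatment effect. All of this stands, and it sets the severity.

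A reader might infer that option (1) only re-reads the allocation. If arm stays in the model, it does not: the level slope comes from variation within the adalimumab arm, and an inert level reaches p<0.05 in only 5 to 6% of trials. The mixing arises in pooled analyses without an arm term, which option (2) and the correlations leave open but do not prescribe.

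A reader might also call the adjusted arm coefficient meaningless, or the level nearly collinear with arm. The first is too strong: the coefficient is a kind of direct effect, but it needs no unmeasured common cause of level and hardness. The second depends on how many participants still have measurable drug about three months after injection, and the documents do not say.

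Finally, complete mediation through serum level is an extreme case. The protocol's rationale is local delivery into the nodule, and serum is sampled to study absorption and injection frequency. So the fall to zero is one end of a range, not a forecast.

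What survives is that a listed method produces an arm estimate that is easily misread, with no population, sampling time or caution attached. SAP 6.6 reserves its post hoc label and 0.01 threshold for analyses not specified, and this one is specified.

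**Conclusion.** The point holds as a minor correction to an exploratory section. A level-adjusted arm coefficient does not estimate the randomised effect, whatever the level distribution; that follows from the level being post-randomisation and expected to be zero on saline. How far it departs depends on assumptions: about 0 under full mediation; a standard error of 1.58 to 4.00 instead of about 1.5 if the level is irrelevant; and -5.1 to -11.7 against a true -5 under the common-cause scenario tried. Pooled analyses without an arm term would flag an inert level in 11 to 84% of trials over the range examined.

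The documents do not support the wider inference that the trial's primary conclusion is at risk: the level is not in that analysis, and the exploration may never be run.

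**What to change.** Amend SAP 6.4 as follows.

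- Replace option (1) with a regression of 12-month hardness on circulating adalimumab level, adjusted for baseline hardness, among participants allocated to adalimumab only.
- Restrict option (2) and the adalimumab-level correlations to the same participants.
- Name the sampling time (3 or 12 months) that supplies the level.
- Label the results as non-randomised associations, and state that no level-adjusted arm coefficient will be reported as a treatment effect.

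Two further steps are optional: adjusting for days since last injection, and running the correlations whether or not a preceding test is significant.

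The cost is SAP wording and an exploratory analysis in about half the participants. Little is lost by that, because once arm is in the model the saline arm contributes essentially nothing to the level slope.

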### Safety analysis

Adverse events are recorded as a secondary outcome in the RIDD RCT.

A Serious Adverse Event (SAE) is any untoward medical occurrence that results in death, is life-threatening, requires inpatient hospitalisation or prolongation of existing hospitalisation, results in persistent or significant disability/incapacity, or consists of a congenital anomaly or birth defect. All potentially related SAEs must be recorded on the trial specific SAE form and reported within 24 hours to the Study Site Team becoming aware of the event. Causality must be assessed by a medically qualified doctor. The SAE form must be sent to the Trials office. The SAE form will also be sent to an independent clinician as soon as all relevant information is available but no later than 3 calendar days from when the trial office is made aware of the event as per OCTRU SOPs for safety reporting. The independent clinician will assess the SAE for causality and expectedness and provide a response as per OCTRU safety reporting. In the event where the independent clinician disagrees with the assessment of the site PI, a discussion will be encouraged between the two to reassess the event. If either the PI or the independent clinician continue to assess the event as related, both assessments will be recorded. If the event is also serious and unexpected this will be reported as a SUSAR by the Trials Office to the MHRA, Ethics and Sponsor as per below. All related SAEs will be followed until resolved or not further information is expected. SAEs will only be considered closed when signed off by the local PI.

The safety analysis will be carried out on the safety population (see **Section 4.2**). Details for any related SAEs and SUSARs will be reported. Should sufficient numbers be reported comparison of patients experiencing related SAEs and SUSARs between the two treatment groups will be undertaken by examining 95% confidence intervals for the difference in incidence. An overall category for any SAE will also be compared.

The injection site will be monitored for adverse events using an 'Injection Site Response' Form, which is collected shortly after receiving each treatment. Frequency and percentages for types of AEs reported will be presented. Where sufficient numbers of AEs are reported, chi-squared tests will be used for comparing intervention groups at each follow-up time-point. *P*-values will be reported to 3 decimal places.

Repurposing anti-TNF for treating Dupuytren's disease (funded by Health Innovation Challenge Fund, Wellcome Trust)

EudraCT Number: 2015-001780-40 and OCTRU Reference Number CTU0028

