#### **Adverse Event monitoring**

**Injection site assessment:** The most common adverse reaction with adalimumab is injection site reactions. The injection site will be monitored for adverse events using an 'Injection Site Response Form'. The injection responses are based on injection site reactions in the prescribing literature and in clinical trials. In placebo-controlled trials in patients with rheumatoid arthritis, 14% of patients treated with adalimumab developed injection site reactions (erythema and/or itching, hemorrhage, pain or swelling), compared to 8% of patients receiving placebo (SmPC for Humira (adalimumab), updated 26 March 2015). Most injection site reactions were described as mild.

**Surgery site assessment (Part 1 only):** The surgery site will be monitored using wound assessment criteria from the Centers for Disease Control and Prevention (CDC; [www.cdc.gov/nhsn](http://www.cdc.gov/nhsn)).

**Progression to surgery of the digit being assessed (Part 2 only):** Progression to surgery of the digit being assessed, if applicable, will be recorded during the 18 month follow-up.

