## 5.2 Withdrawal from treatment and/or follow-up

The numbers (with percentages) of losses to follow-up (defaulters and withdrawals) will be reported and compared between the adalimumab and saline groups. To ensure that there are not differential losses between the groups this will be tested using absolute risk differences and associated 95% confidence intervals, and a Chi-squared test. Any deaths (and their causes) will be reported separately.

**Appendix 5: Trial recruitment, Table 1:** Patient withdrawals and reasons according to intervention groups.

**Appendix 5: Trial recruitment, Table 2:** Number of participants with data available at each time-point by intervention allocated.

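### Injection-site reactions in Part 2 are compared only by unadjusted visit-by-visit chi-squared tests, with no risk difference, confidence interval or per-participant summary specified

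*SAP*

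**What the plan says.** The Safety analysis in SAP section 6.4 opens with "Adverse events are recorded as a secondary outcome in the RIDD RCT". Reactions are recorded on an injection-site form after each treatment. For these data it plans a description, "Frequency and percentages for types of AEs reported will be presented", and one comparison, "Where sufficient numbers of AEs are reported, chi-squared tests will be used for comparing intervention groups at each follow-up time-point", with P-values to three decimals. It sets no threshold for sufficient numbers, does not adjust across visits, and does not say whether the baseline injection counts as a follow-up time-point.

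Other parts of the SAP go further:

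- Related SAEs, in the same section, are compared "by examining 95% confidence intervals for the difference in incidence".
- For losses to follow-up (section 5.2), "this will be tested using absolute risk differences and associated 95% confidence intervals, and a Chi-squared test".
- Section 4.1 states: "Secondary outcomes will also be analysed using a significance level of 5% and 95% confidence intervals".
- Section 6.3 analyses secondary outcomes by mixed-effects models over all time-points (logistic if binary). The change log (section 1.2) records that this replaced analysis at individual time-points.

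The Appendix 5 shell tables include none for adverse events.

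The only reaction rates are in the Protocol, section 4, Adverse Event monitoring. In placebo-controlled rheumatoid arthritis trials, "14% of patients treated with adalimumab developed injection site reactions", against 8% on placebo.

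**The concern.** Comparing adverse events between arms is a stated secondary objective of Part 2. Other adverse-event recording is narrow: Protocol section 10.3 asks only for events of grade 3 or above attributed to the drug or its injection. The injection-site form is therefore the main systematic source on harm.

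A chi-squared P-value gives neither the size of an excess nor the largest excess compatible with the data. Testing each visit separately splits the information into four weak comparisons and gives chance four opportunities to produce a significant result. Making the test depend on an undefined count leaves open, until the data are seen, whether any comparison is made. A scatter of visit-level P-values could be taken as reassurance when an excess exists, or as a signal when none does.

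**Working it through.** **Inputs**

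- Arm sizes: 69 (the stated minimum of 138) and 100 (the maximum of 200), 1:1 allocation (Protocol sections 6 and 11.3).
- Two-sided 5% level (SAP 4.1; Protocol 11.3 for two-sided).
- Rates: 8% and 14% (Protocol section 4).
- Four injection visits: baseline, 3, 6 and 9 months.
- Assumptions: full arms at every visit, and within-person correlation of reactions between 0 and 0.5. The documents give neither a reaction rate for injection into the nodule nor a correlation.

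**The plan's own figure.** For nodule hardness, d = 5/8 = 0.625. The two-sample t-test at 90% power needs 55 per arm, and 55/0.80 = 68.75, so 69 per arm and 138 in total. This reproduces the plan. No sample size or power is stated for injection-site reactions.

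**Power of one visit's test, 14% v 8%.** The mean rate is 0.11.

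- Standard error under no difference: s0 = √(2 × 0.11 × 0.89 / n).
- Standard error under the alternative: s1 = √((0.08 × 0.92 + 0.14 × 0.86) / n).
- Power ≈ Φ((0.06 − 1.96 × s0) / s1).

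| n per arm | s0 | s1 | Approximate power | Exact enumeration |
|---|---|---|---|---|
| 69 | 0.0533 | 0.0530 | Φ(−0.84) = 20% | 20% |
| 100 | 0.0442 | 0.0440 | Φ(−0.61) = 27% | 28% |

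**False signal over four tests with no true difference.** With independent tests, 1 − 0.95⁴ = 18.5%. Simulation of the chi-squared test at 8% in both arms gives 17-20% for correlations of 0 to 0.5. A fifth test, at the 12-month assessment, would give 1 − 0.95⁵ = 22.6% under independence.

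**At least one significant test, if 14% v 8% are per-injection rates.** With independent visits this is 1 − (1 − 0.201)⁴ = 59% at 69 per arm and 1 − (1 − 0.277)⁴ = 73% at 100 per arm. With correlation 0.3, simulation gives about 51% and 64%.

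**The same, if 14% v 8% are the shares of patients who ever react.** With independent injections the per-visit rates are 1 − 0.92^(1/4) = 2.1% and 1 − 0.86^(1/4) = 3.7%. The expected counts at 69 per arm are then about 1.4 and 2.6. For correlations of 0 to 0.5, power per visit is 7-12% (69 per arm) or 9-15% (100 per arm). At least one of four tests is significant in about 25-31% or 33-37% of trials.

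**What an interval would show.** The half-width of the 95% CI for a risk difference at 14% v 8% is 1.96 × s1.

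- 69 per arm: 10.4 points, so an expected interval of −4.4 to +16.4.
- 100 per arm: 8.6 points, so −2.6 to +14.6.

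With 8% in both arms the half-width is 9.1 or 7.5 points.

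**Power of one participant-level comparison (any reaction).** If the rates are per injection, about 41-54% at 69 per arm and 54-70% at 100 per arm (correlation 0.3 to 0). If the rates are per patient, about 20% and 28%. Its false-positive rate is about 5%.

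**The case against.** The strongest reply is that the gap is mostly one of wording. SAP 4.1 already provides 95% intervals for secondary outcomes and nothing in the Safety analysis withdraws that. Percentages by type of event are shown whatever the test says. Injection pain, itself one of the listed reactions, is analysed by mixed-effects regression over all four injections with a mean difference and 95% CI. Requiring sufficient numbers before a chi-squared test is an ordinary safeguard. Much of this stands. It does not say which quantity the interval would be for, at which visit or over which period, and no shell table fills the gap. The pain score does not cover erythema, itching, haemorrhage or swelling.

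A reader might infer that a real excess would usually go undetected. That is true of each test. For the set it depends on the base rate: on the per-injection reading at least one test is significant in more than half of trials, which is more often than the participant-level comparison would be. Part of that detection is bought with the inflated false-signal rate, so power is not a reason for the change.

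A reader might also infer that the plan will take a non-significant result as evidence of local safety. Neither document says so, and SAP 4.1 calls secondary outcomes supportive only. The risk is one of misreading.

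Finally, Protocol section 6 (Part 2) allows an injection to be omitted when the nodule has shrunk. If that happens more in one arm, a proportion with any reaction over injections received compares unequal exposure. This objection stands, and the fix has to address it.

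**Conclusion.** The point holds as a defect of specification. The only comparison named for this harm is a set of unadjusted visit-level P-values that run on an undefined condition and estimate nothing. This falls short of the SAP's own handling of related SAEs and losses to follow-up, and no shell table carries out the general promise of intervals.

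Its size is single-visit power of about 20% (69 per arm) or 28% (100 per arm) for 14% v 8%, and about an 18% chance of at least one false signal over four tests. The false-signal figure is the firmer one, because it depends little on the assumed rate or correlation. The power figures rest on carrying per-patient rates from another disease over to single injections into a nodule, which is an assumption. The documents do not support a claim that an excess would necessarily be missed. They support the narrower conclusion that the planned output could mislead in either direction and would not show how large an excess remains possible.

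**What to change.** In the Safety analysis of SAP section 6.4:

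1. Make the single between-arm comparison the proportion of safety-population participants with at least one injection-site reaction over all injections received, including the baseline injection. Report it as a risk difference with a 95% CI whatever the counts, and add a shell table for it.
2. Keep visit-level frequencies by type as descriptive tables without P-values, with the number injected at that visit as the denominator.
3. Show the number of injections received and the per-injection reaction rate by arm beside the main comparison, because omitted injections can make exposure unequal.
4. State that a non-significant difference is not evidence of local safety.

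The data are already collected, so the cost is SAP wording and a small amount of tabulation. Visit-level P-values are lost. The change does not make the trial large enough: at 14% v 8% the interval still extends about 9-10 points either side of the estimate. It holds the false-signal rate near 5% and shows how much excess has not been excluded.
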